14.9 Indemnity

The Sponsor has foreseen an insurance policy for this trial as set out in the Law of 2004 through Amlin Europe NV, in collaboration with Vanbreda Risks & Benefits NV, with contract number 299.053.700. The Sponsor shall throughout the duration of the study effect and maintain this insurance policy providing an adequate level of cover in respect of all risks which may be incurred by the Sponsor arising out of the Sponsor's performance of the study.

The terms or the amount of cover of any insurance shall not relieve the Sponsor of any liabilities under the clinical trial agreement.

14.10 Access to the Study Data by KCE and similar institutes in the EU

This section should be read in conjunction with the research agreement, which supersedes the protocol in case of contradictory statements.

A distinction is to be made by access by KCE (and similar institutes in Europe) and access by other parties.

Access to Study Data by KCE is fully defined in the contract between KCE and the Sponsor and the research agreement template is publicly available on the KCE website. Link: https://kce.fgov.be/en/resources-for-investigators

14.11 Access to the final trial dataset by other parties

The study results will be owned by the party who generates them. The Sponsor will have access to the study data. At the end of the study, KCE will receive from Sponsor specific study data. This will only be anonymous study data or, where requested by KCE, coded personal data are made available to KCE.

The study data shall not be provided to a third party without the prior written approval of KCE, which approval KCE shall not unreasonably withhold or delay and which KCE may subject to specific conditions in order to ensure that the provision of said study data does not have a negative impact on the further performance of the study, the rights granted to KCE under the research agreement and/or the benefit of the Study for the patients and/or the public payers.

15 DISSEMINATION POLICY

15.1 Dissemination policy

This section should be read in conjunction with the research agreement, which supersedes the protocol in case of contradictory statements.

The results of the study shall be owned by the party who generates them.

The results of the study owned by Sponsor and/or (where applicable) any collaborator shall be disseminated as soon as possible, by disclosing them to the public by appropriate means, including in scientific publications (in any medium). Sponsor shall inform and discuss its dissemination strategy with KCE in advance.

The final Study report should be made available for review by KCE before the results are disseminated. KCE shall be notified prior to any dissemination (including publication) (whether in oral, written or other form) of the foreground IP or results or study data or of matters arising from the study. The Chief Investigator shall send one draft copy of the proposed dissemination to KCE at least ten (10) days for an abstract and thirty (30) days for a manuscript before the date intended for dissemination. For the avoidance of doubt, this obligation continues after the end of the study. KCE may object within thirty (30) days of receiving notification, if, in its reasonable opinion, the dissemination (or the timing thereof) is not in the public interests. In the event Chief Investigator or (where applicable) any collaborator intends not to protect the results of the study it needs to formally notify KCE thereof before the dissemination takes place, Sponsor shall ensure that any dissemination is scientifically correct, objective and unbiased (taking into consideration the primary endpoint(s)).

In the event of a multicentre study, Sponsor nor its collaborators shall independently publish or otherwise disclose any findings resulting from the study before publication of the main multicentre publication.

Any dissemination shall acknowledge KCE's financial support and carry a disclaimer as KCE may require in accordance with the clinical trial agreement.

Open access will be ensured (free of charge, online access for any user) to all peer-reviewed scientific publications relating to the results of the study owned by it and/or the collaborators. In particular, Sponsor shall: (i) As soon as possible and at the latest on publication, deposit a machine readable electronic copy of the published version or final peer-reviewed manuscript accepted for publication in a repository for scientific publications; moreover Sponsor must aim to deposit at the same time the research data needed to validate the results of the study presented in the deposited scientific publications; and; (ii) Ensure open access to the deposited publication, via the repository at the latest on publication (if an electronic version is available for free via the publisher) or, within six (6) months of publication in any other case.

We will ensure that the findings of the study will be disseminated to relevant stakeholders other than the scientific world including the general public, health care providers and policy makers. Therefore, information about the study will be spread through websites (news sites of the universities, medical and health information sites such as gezondheid.be), newsletters and press releases. Next, we will inform agencies such as BAPCOC, insurance

companies and patient representative groups (Vlaams Patiënten Platform, LUSS) and encourage them to further circulate the information through their own communication channels. Furthermore, the results will be presented to various government bodies and policy makers and on conferences and on local seminars for general practitioners (LOKs, GLEMs). Finally, the study findings will be published in national journals (for example HANU, Revue de la Médicine Générale).

In case this study proves our diagnostic algorithm to be more effective than usual care to reduce antibiotic prescribing rate in children, translating this evidence into routine practice will be the next great challenge.

Though the development of an implementation strategy is clearly beyond the scope of this study, we would like to formulate some general recommendations/considerations.

- the implementation intervention strategy should be developed based upon a theoretical framework applying a systematic approach (Vis 2015). Multiple theories and frameworks exist but one common ingredient comprises an in-depth analysis of the perceptions, barriers and facilitators as experienced by all stakeholders. The process evaluation that is part of this trial will be informative in respect to this and hence provide a basis for an implementation strategy.
- it will be essential to educate physicians about introducing the diagnostic algorithm including POC CRP testing and safety netting advice in their daily practice. This will require training which should be delivered through accredited Continued Medical Education (CME) but should also be part of the basic medical curriculum for physicians. The engagement of the majority of the Belgian academic centres for general practices in this trial will undoubtedly facilitate the integration of education about diagnosis and management of infectious diseases in children in ambulatory care –in combination with antibiotic prescribing guidelinesin the medical curriculum.

15.2 Authorship eligibility guidelines and any intended use of professional writers

All reports will be written by researches directly involved in the study and supervised by the Steering Committee. Only researchers or participants actively involved in parts of the study will be eligible for authorship.

APPENDIX 1. RISK ASSESSMENT OF THE TRIAL INTERVENTION(S)

Risks associated with trial interventions

 \boxtimes A = Comparable to the risk of standard medical care

 \square B = Somewhat higher than the risk of standard medical care

 \Box C = Markedly higher than the risk of standard medical care

Justification: Briefly justify the risk category selected and your conclusions below (where the table is completed in detail the detail need not be repeated, however a summary should be given):

The risk of adverse events occurring as a consequence of the intervention in this trial is unlikely therefore safety reporting will be limited to the safety reporting that is necessary in routine care

How will these risks be minimised?			
-			

Outline any other processes that have been put in place to mitigate risks to participant safety (e.g. DMC, independent data review, etc.)

Outline any processes (e.g. IMP labelling +/- accountability +/- trial specific temperature monitoring) that have been simplified based on the risk adapted approach.

ARON TRIAL – STATISTICAL ANALYSIS PLAN

Impact of a diagnostic algorithm including clinically guided point-of-care C-reactive protein testing and safety netting advice on antibiotic prescribing rate and further management of acutely ill children presenting to ambulatory care: multicentre, clusterrandomized, parallel group pragmatic trial (the ARON project)

This statistical analysis plan provides guidelines for the final presentation and analysis for the ARON trial. This plan, along with all other documents relating to the analysis of this trial, will be stored in the Trial Master File electronically and/or in hard signed copy formats.

[name] [name] [contact] Department of Public Health and Primary Care, KU Leuven	Chief Investigator
[name] [name] [contact] Department of Public Health and Primary Care, KU Leuven	Project manager
[name] [contact] Leuven Biostatistics and Statistical Bioinformatics Centre, KU Leuven	Trial statistician with final responsibility on trial analysis. She will validate the analysis for the primary outcome.
[name] [contact] Department of Public Health and Primary Care, KU Leuven	Scientific collaborator who will perform the primary analysis as well as part of the secondary analysis.
[name] [contact] Department of Public Health and Primary Care, KU Leuven	Scientific collaborator who will perform part of the secondary analysis, the full process evaluation as well as the health economic analysis.

Approval of statistical analysis plan

The undersigned confirm that the following SAP has been agreed and accepted:

[name] Date: Signature: [name] [name] Date: Signature:

Overall aim and research question

Background. The ARON trial will test the impact of a diagnostic algorithm including a standardized clinical assessment, a point-of-care (POC) C-reactive protein (CRP) test, and safety netting advice.

Question. Is this diagnostic algorithm able to safely reduce antibiotic prescribing in acutely ill children presenting to ambulatory care?

Aim. To establish the assumed superiority of a diagnostic algorithm including a standardized clinical assessment, a POC CRP test and safety netting advice over usual care to reduce antibiotic prescribing rates (both immediate and delayed prescribing).

Design of the trial

This study is a multicentre, pragmatic cluster-randomized controlled superiority trial:

- multicentre: six academic centres for primary care will be involved in the recruitment of 122 primary care practices
- pragmatic: criteria excluding patients from participation will be limited as well as procedures that do not reflect care as usual
- cluster: randomization occurs at the level of the primary care practice while patients are the unit of analysis
- randomized: block randomization per academic centre will be performed to assign primary care practices to either the intervention or the control arm
- controlled: the intervention will be compared with usual care
- superiority: the trial is designed to show that the intervention is superior to usual care

Randomization

In order to avoid contamination between physicians working in the same practice, randomization will happen at the level of the physician's practice.

General practice clinics and community paediatric centres will be randomized in one of the two study arms in a 1:1 ratio using a block randomization system stratified per recruiting academic centre in order to guarantee that allocation to either the usual care or the intervention arm is balanced within every region.

Stratified block randomization will be done using an electronic random numbers generator in blocks of four practices. Randomization and concealment will be centralized at the KU Leuven and conducted by a staff member not involved in data collection or delivering the intervention.

Sample size calculation

The original sample size calculation in the approved protocol version 2.0 was based on previous data from the ERNIE2 trial, assuming an overall antibiotic prescribing proportion of 26.5% in those children recruited for our trial.

The overall antibiotic proportion was found to be 18% in the first 4938 patients recruited in the ARON trial.

If we were to assume a reduction of 5.3% (proportionate to our original reduction) between the usual care group and the intervention group, using a 5% significance level (alpha 0.05), an intracluster correlation coefficient (ICC) of 0.063 (based on data from the ERNIE2 trial in the exact same population), and power of 90% (beta 0.1), this would require 63 clusters of 50 patients in both arms, resulting in 6300 children.

R code:

We used the n4props-function in the R package CRTSize, using the following command: n4props(pc = 0.2065, pe = 0.1435, m = 50, ICC = 0.063, alpha = 0.05, power=0.9, AR=1, two.tailed=TRUE, digits=3).

Considering the pragmatic nature of this trial and in correspondence with the 10% of practices performing non-consecutive inclusion of patients (high risk of selection bias) during the ERNIE2 trial, we will perform sensitivity analyses only considering physicians who have recruited in a consecutive way. Taking into account the required sample size for this analysis of the primary study outcome, these assumptions result in a total sample size of 7000 patients.

Timing of the analysis

- Primary and secondary outcomes: April June 2024.
- Health economic study: January February 2025. This timeline is contingent upon possible delays in data availability from IMA and the efficiency of the data retrieval process.

Withdrawals

Withdrawal from the study can be initiated either by the child, their parent(s), or by the physician. As stated in the Informed Consent Form, children and their parents have the right to end their participation in the trial at any point in time and for any reason. In case a child or parent wishes to end their participation, they can do so by notifying their physician.

The treating physician can also consider a child for withdrawal from the study. However, the physician will have to discuss this option with the study coordinator and receive the consent of the latter before a final decision of withdrawal can be made.

In all instances, the reason for withdrawal will be asked for and recorded, but participants/parents are not required to share their reason for withdrawal.

Withdrawn children will not be replaced.

The patient and/or parent/legal guardian may withdraw consent at any time during the study. For the purposes of this trial, withdrawal is defined as:

The patient and/or parent/legal guardian would like to withdraw consent from study and is not willing to be followed up for the purposes of the trial at any further visits (i.e., only data collected prior to the withdrawal of consent can be used in the trial analysis).

The details of withdrawal should be clearly documented in the patient's health records and in the electronic case report form (REDCap).

Software used

REDCap version 13.7.25 (2024 Vanderbilt University).

QSR NVIVO software version 12 (QSR International Pty Ltd, Melbourne, Australia). R software version 4.2.3 (1) within R Studio (2023.12.1 Build 402) (2) using the 'glmer' function of the 'lme4' package (3) and the 'n4props' function of the 'CRTSize' package (4).

(1) R Core Team (2023). R: A language and environment for statistical computing. R Foundation for Statistical Computing, Vienna, Austria. URL https://www.R-project.org/.

(2) Posit team (2023). RStudio: Integrated Development Environment for R. Posit Software, PBC, Boston, MA. URL http://www.posit.co/.

(3) Douglas Bates, Martin Maechler, Ben Bolker, Steve Walker (2015). Fitting Linear Mixed-Effects Models Using lme4. Journal of Statistical Software, 67(1), 1-48. doi:10.18637/jss.v067.i01.

(4) Rotondi MA (2023). _CRTSize: Sample Size Estimation Functions for Cluster Randomized Trials_. R package version 1.2, <https://CRAN.R-project.org/package=CRTSize>

Interim analyses

No interim analyses are planned.

Data Source

Our study utilized a prospective data collection approach, drawing from several sub-databases to create a comprehensive dataset for analysis:

1. **REDCap Database.** A secure web application for building and managing online surveys and databases. REDCap was utilized for its robust data capture capabilities, particularly for complex longitudinal data and multisite clinical research studies.

2. ARON App Database. A user-centred database collected through direct patient/parent contact via a mobile application over a 30-day follow-up period. These data encompass information on daily symptoms, healthcare consultations, hospital visits, and health-related quality of life (HRQoL).

3. Administrative Database (healthcare utilization). Data obtained from the Intermutualistische Agentschap (IMA) on potential hospitalizations, technical provisions, and reimbursed pharmaceutical usage up to 3 months post-index consultation. Access to this administrative data for ARON participants is enabled by a secure procedure developed to transmit national insurance numbers in compliance with GDPR regulations, facilitated by a trusted third party. This data is collected for all ARON trial participants with valid national insurance numbers.

4. Interview Transcripts. A process evaluation is nested within the ARON trial, aiming to gather insights into the utilization and perceptions of the intervention by physicians and (parents of the) patients. This qualitative process evaluation entails conducting individual semi-structured, in-depth interviews with GPs and parents, facilitated through video conferencing.

Date of final version of dataset

1. REDCap Data

Estimated date of receipt 29/03/2024.

2. ARON App Data

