Contact Datum Is kleiner dan of gelijk aan 31/10/2022 ARON 2.En de periode dat ze gerekruteerd hebben tijdens de trial (gemakkelijk te vinden in Redcap - bv 1 mei 2021 t/m 30 november 2022). b.Hoeveel kinderen hebben minstens 1 AB voorschrift gekregen						
Medicatie	BCFI boom	ls gelijk aan	Antibacteriële middelen			
Contact	Datum	ls kleiner dan of gelijk aan	31/10/2022			
Patiëntenadministratie	Geboortedatum	ls kleiner dan of gelijk aan	30/11/2020			
Contact	Datum	ls groter dan of gelijk aan	01/05/2021			
Medicatie	Datum	ls groter dan of gelijk aan	01/05/2021			
Patiëntenadministratie	Geboortedatum	ls groter dan of gelijk aan	01/05/2009			
Contact	Auteur	ls gelijk aan				
Contact	Туре	ls gelijk aan	Consultatie			
Medicatie	Datum	ls kleiner dan of gelijk aan	31/10/2022			

Figure 8. Audit questions (after start of the trial) in CareConnect software (Corilus).

Most software packages, e.g., CareConnect², Daktari³, HealthOne⁴, of which the former dominate the market, have a statistics/search module. This allows for easy and uniform access to the required data.

2. Sample size calculation

The original sample size calculation was based on previous data, assuming an overall prescribing rate of 26.5% in those children recruited for our trial.

The overall prevalence was found to be 18% overall in children recruited in the first 4938 patients recruited in the ARON trial.

If we were to assume a reduction of 5.3% (proportionate to our original reduction) between the usual care group and the intervention group, using a 5% significance level (alpha 0.05), an intracluster correlation coefficient (ICC) of 0.063 (based on data from the ERNIE2 study in the exact same population), and power of 90% (beta 0.1), this would require **63 clusters of 50 patients** in both arms, resulting in **6300 children**.

R code:

We used the n4props-function in the R package CRTSize, using the following command:

n4props(0.2065,0.1435,50,0.063, alpha = 0.05, power=0.9, AR=1, two.tailed=TRUE, digits=3)

Considering the pragmatic nature of this trial and in correspondence with the 10% of practices performing nonconsecutive inclusion of patients (high risk of selection bias) during the ERNIE2 trial, we will perform sensitivity analyses only considering physicians who have recruited in a consecutive way. Taking into account the required sample size for this analysis of the primary study outcome, these assumptions result in a total sample size of 7000 patients for the primary study outcome.

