11.3.4 Procedure(s) to account for missing or spurious data

Drop-outs are unlikely to be a large problem since there will be only 1 study visit complemented by the collection of follow-up information.

We will analyze the whole population for the primary analysis and perform a sensitivity analysis excluding the low recruiting practices (less than 10 patients recruited during 12 months) to avoid our results to be susceptible to selection bias. In previous trials this resulted in approximately 5% of practices who did not contribute to these sensitivity analyses as the risk of selection bias was deemed extremely high in these practices.

Practices that do not recruit children at all will be stopped after the first two monitoring visits and replaced by new practices to avoid reducing the total number of clusters, available for analysis.

See section 8.6 for strategies to maximize follow-up and to prevent missing data. See sections 11.3.2 and 11.3.3 for statistical handling of missing data.

The percentage of missing data for the primary outcome measure of antibiotic prescribing rate is expected to be low as this will be registered at the first-contact consultation. In our previous trial, we found 4% of missing data for the primary outcome of antibiotic prescribing rate. Multiple imputation will be considered for the primary outcome measure as well as missing values for patient-reported outcomes (if there are any). Other outcomes will be collected in the patient health record of the physician.

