Drop-outs are unlikely to be a large problem since there will be only one study visit complemented by the collection of follow-up information.

We will analyse the whole population for the primary analysis and perform a sensitivity analysis excluding the low recruiting practices (less than 10 patients recruited for 12 months) to avoid our results to be susceptible to selection bias. In previous trials this resulted in approximately 10% of practices.

Practices that do not recruit children at all will be stopped after the first two monitoring visits and replaced by new practices to avoid reducing the total number of clusters available for analysis.

The percentage of missing data for the primary outcome of antibiotic prescribing proportion is expected to be low as this will be registered at the first contact consultation. In our previous ERNIE2 trial, we found 4% of missing data for the primary outcome of antibiotic prescribing proportion. Multiple imputation will be considered for the primary outcome measure as well as missing values for patient-reported outcomes (if there are any). Other outcomes will be collected from the patient health record of the physician.

Multiple imputation will be applied to deal with missing data. Imputation will be performed for the binary outcome variable and logistic regression will be used as imputation model. Predictors for the imputation model are baseline patient characteristics and intervention.

2. ARON App Data

A substantial drop-out rate in app completion is anticipated, with non-completion of the app not considered grounds for exclusion from the study. To address this, proactive measures were introduced to enhance participation rates, such as the provision of information about the smartphone app and instructions on installation to children and their parents during the baseline consultation. Additionally, the app was made available in three languages (Dutch, French, English).

Multiple imputation will be applied to deal with missing data. For imputation of continuous variables, a linear regression model will be employed, with baseline patient characteristics and intervention serving as predictors for the imputation model.

3. Administrative Data

Multiple imputation, following Rubin's rules, will be utilized to address missing data. Predictors for the imputation model will include baseline patient characteristics and the intervention.

4. Interview Transcripts

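### The step from 6300 to 7000 children adds children but not practices, so it does not keep 90% power in the sensitivity analysis it is meant to protect; 90% for the primary analysis is plausible but not shown

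*SAP*

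**What the plan says.** The SAP (Sample size calculation) and Protocol 11.1.2 size the trial with a single fixed practice size. The SAP's command begins "n4props(pc = 0.2065, pe = 0.1435, m = 50, ICC = 0.063" and asks for 90% power, two-sided 5%. It returns 63 practices per arm; in the SAP's words, "this would require 63 clusters of 50 patients in both arms, resulting in 6300 children".

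Both documents then recall that 10% of practices in the preceding trial did not recruit consecutively, and announce a sensitivity analysis restricted to consecutive recruiters. On that ground the protocol concludes that "these assumptions result in a total sample size of 7000 patients for the primary study outcome".

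The number of practices is 122 in Protocol sections 5 and 6 and in the SAP (Design of the trial). Protocol 11.2 gives 122 physicians and a recruitment period of 21 months.

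The primary analysis uses the whole population. Protocol 11.3.4 adds a sensitivity analysis "excluding the low recruiting practices (less than 10 patients recruited during 12 months"). On how many that would be, the protocol says "In previous trials this resulted in approximately 5% of practices". The SAP (Handling of missing values and other data conventions), for the same rule, says "In previous trials this resulted in approximately 10% of practices". Neither document gives a CV for practice size or a distribution of practice sizes.

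**The concern.** With an ICC of 0.063 and about 50 children per practice, power depends mainly on how many practices there are. Extra children in the same practices add little. An allowance for losing 10% of practices therefore has to be made in practices: 126/0.9 = 140. The plan makes it in children and leaves the practice count at 122. That figure matches the superseded total (6111/50 = 122.2), so it may simply not have been updated; this is an inference.

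A second, smaller issue is that the design effect assumes equal practices, while the plan itself expects some to recruit fewer than 10 children a year against a design value of 50, and keeps them in the primary analysis. Unequal sizes lower power.

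What is at stake is the stated 90%, and the sensitivity analysis on which the plan relies against selection bias. An accurate power figure matters most if the result is null or if the two analyses disagree.

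**Working it through.** **Inputs.** From the R command: pc = 0.2065, pe = 0.1435, difference 0.063, m = 50, ICC = 0.063, two-sided alpha 0.05, power 0.90. From the text: 122 practices, 7000 children, 21 months, exclusion of 5% or 10% of practices. Assumed, because the documents give none: CV of practice size 0.4-0.8.

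**Formulas.**
- Variance sum V = pc(1-pc) + pe(1-pe) = 0.1639 + 0.1229 = 0.2868.
- Power = Phi(0.063/SE - 1.96), with SE = sqrt(V/n_eff) and n_eff the effective number per arm.
- Equal sizes: n_eff = n/DE, DE = 1 + (m-1) x ICC.
- Unequal sizes, conservative: DE = 1 + [(1+CV^2)m - 1] x ICC.
- Unequal sizes, efficient weighting (closer to a mixed model): n_eff = sum of m_i/(1 + (m_i-1) x ICC), with gamma-distributed sizes for a given CV.

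**1. The plan's own figure.** DE = 1 + 49 x 0.063 = 4.087. Practices per arm = (1.960 + 1.2816)^2 x 0.2868 x 4.087/(50 x 0.063^2) = 62.05, rounded up to 63. So 63 x 50 x 2 = 6300 reproduces, with power 90.4%. The next step is 6300/0.9 = 7000 exactly.

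**2. Practices needed after a 10% loss.** 7000/50 = 140, and 140 x 0.9 = 126. The plan has 122, and 122 x 0.9 = 109.8, about 110 (55 per arm).

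**3. Sensitivity analysis, equal sizes.** Low recruiters have fewer than 10 x 21/12 = 17.5 children, so at most 17 each. Removing 12 of them leaves at least 7000 - 12 x 17 = 6796 children. The plan's own arithmetic implies 6300.

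| Practices left | Children left | Mean size | DE | n_eff per arm | Power |
|---|---|---|---|---|---|
| 110 (10% excluded) | 6300 | 57.3 | 4.545 | 693 | 87.2% |
| 110 (10% excluded) | 6796 | 61.8 | 4.83 | 704 | 87.7% |
| 116 (5% excluded) | 6650 | 57.3 | 4.549 | 731 | 88.9% |

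Keeping almost 500 more children in the same 110 practices gains half a percentage point.

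**4. Sensitivity analysis, unequal sizes (110 practices, 6300 children).** At CV 0.4, 0.6 and 0.8, efficient weighting gives 86.3%, 85.0% and 83.1%. The conservative form gives 83.1%, 78.0% and 71.3%.

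**5. Primary analysis, 7000 children in 122 practices (mean 57.4).**

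| Practice sizes | Efficient weighting | Conservative DE |
|---|---|---|
| Equal | 90.4% | 90.4% |
| 10% of practices at 17 children, rest equal (CV 0.23) | 89.8% | 89.2% |
| 10% at 5 children, rest equal (CV 0.30) | 88.9% | 88.3% |
| CV 0.4 (assumed) | 89.6% | 86.7% |
| CV 0.6 (assumed) | 88.5% | 82.0% |
| CV 0.8 (assumed) | 86.7% | 75.7% |

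With 5% of practices at 17 children the CV is 0.16, and power is about 90% under both forms.

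**6. The ICC.** For 126 equal practices of 50, power is 97% at ICC 0.04, 90% at 0.063, 85% at 0.08 and 78% at 0.10. The re-estimation took the prescribing rate from the first 4938 children but kept the ICC from the earlier trial. The same children can supply the ICC and the practice sizes without arm labels.

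**The case against.** A reader might infer that the trial fails to deliver 90% power for its primary outcome, with 76-82% as the true figure. The documents do not support that. Those values need both an assumed CV of 0.6-0.8 and a design effect that weights practices by size. The SAP (Primary endpoint) specifies a mixed-effects logistic model with clustering by practice, which weights practices close to efficiently and gives about 87-90% over CV 0.4-0.8. The only size pattern the documents describe costs about one point. The shortfall of 122 against 126 practices costs the primary analysis nothing, because 7000 children in 122 equal practices still give 90.4%. Loss of practices does not touch it either: every practice is kept, and those recruiting no one are replaced. All of this stands.

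Nor do the documents show that an ICC of 0.063 is wrong. It could be lower, which would raise power. Estimating it is a check on an influential input, not the correction of an error.

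Two further objections stand in part. First, the SAP's per-protocol rule works on physicians, so fewer whole practices might be lost. But Protocol 8.4 wants only one or two physicians per practice, 11.3.4 excludes practices, and the per-protocol rule adds two further grounds for exclusion. Second, with analysis planned for April-June 2024, the confidence interval will convey precision better than any restated power. That limits the consequence but does not make the stated figure right. Two or three points in a supportive analysis is a modest loss.

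**Conclusion.** The concern holds in a limited form. The 7000 target does not give the sensitivity analysis the 90% power it was set to protect. With 10% of the 122 practices excluded, power is about 87-88% at equal sizes (89% if 5% are excluded), and about 83-87% under efficient weighting if the CV is 0.4-0.8. The equal-size figures need no assumption beyond the plan's own inputs.

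For the primary analysis, 90% is met with equal sizes and holds to within about one point for low recruiters at 17 children each. If sizes vary more, it is about 87-90% under efficient weighting and 76-87% under the conservative form. So 90% is not shown to hold, which is weaker than saying it fails.

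Every figure here uses the command's 6.3-point difference. The adjoining text in both documents states 5.3%. That is a separate and larger matter: at 20.65% versus 15.35%, 63 practices of 50 per arm give about 77%.

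**What to change.** 1. Settle the 5.3 versus 6.3 point difference first, because any restated power depends on it.
2. From the children already recruited, blinded to arm, estimate the ICC and the distribution of practice sizes.
3. Restate power at the actual number of practices, separately for the primary analysis and the sensitivity/per-protocol analysis. Use a calculation that matches the mixed model, with the conservative design effect as a lower bound.
4. Give one figure for the expected share of low-recruiting practices in Protocol 11.3.4 and the SAP, and say whether exclusion applies to practices or to physicians.

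The cost is a short blinded calculation and a slightly less favourable power statement. No extra patients are needed and no planned analysis changes.
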